**Table 11-3 Threshold Analysis Criteria for Laboratory Tests (as applicable)**

Parameter	Threshold Analysis	Comments
GGT	>ULN - ≤ 2.5xULN >2.5x - ≤ 5xULN >5x - ≤ 20xULN >20xULN	CTCAE grade 1-4
Clinical Chemistry (NON-LFT)		
Albumin	<LLN - ≥ 30 g/L <30 - ≥ 20 g/L <20 g/L	CTCAE grade 1-3
Amylase	>ULN - ≤ 1.5xULN >1.5x - ≤ 2xULN >2x - ≤ 5xULN >5xULN	Criteria based upon CTCAE
Creatinine	>ULN - ≤ 1.5xULN >1.5x - ≤ 3xULN >3x - ≤ 6xULN >6xULN	CTCAE grades 1-4
Lipase	>ULN - ≤ 1.5xULN >1.5x - ≤ 2xULN >2x - ≤ 5xULN >5xULN	Criteria based upon CTCAE
Total protein	<LLN >ULN	No CTCAE
Creatine Kinase	>ULN - ≤ 2.5xULN >2.5x - ≤ 5xULN >5x - ≤ 10xULN >10xULN	CTCAE grades 1-4
Hematology		
Hemoglobin	Hgb decreased (anemia) <LLN - ≥ 100 g/L <100 - ≥ 80 g/L < 80 g/L	CTCAE grade 1-3
	Hgb increased >ULN - ≤ 20 g/L above ULN >20 g/L above ULN - ≤ 40 g/L above ULN >40 g/L above ULN	CTCAE grade 1-3
Platelets	Platelet decreased <LLN - ≥ 75.0 x 10e9 /L <75.0 - ≥ 50.0 x 10e9 /L <50.0 - ≥ 25.0 x 10e9 /L <25.0 x 10e9 /L	CTCAE grade 1-4
	Platelet increased >ULN	No CTCAE available
Reticulocytes/Erythrocytes (%)	<LLN >ULN	No CTCAE

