### **12.3.4 Safety Analysis**

All safety analyses will be based on the data from the TE period for the Treatment Period for all subjects in the corresponding Safety Set for the Treatment Period, unless otherwise specified.

The overall safety profile of study drug will be assessed in terms of the following safety and tolerability assessments:

- Treatment-emergent adverse events (TEAEs)
- Clinical laboratory values (i.e., hematology, serum chemistry, coagulation, and urinalysis as applicable)
- Standard 12-lead ECGs
- Vital signs
- Pulse oximetry
- Ophthalmological examinations

Only descriptive analysis of safety will be performed and no statistical testing will be performed. The safety data during the Run-in Period will only be presented in listings, unless otherwise specified. Additional details will be provided in the SAP.

LFT elevations, creatine kinase elevations, rash, cataracts, hypoglycemia, and neuropsychiatric events will be designated as AEs of special interest.

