#### **8.4.2 Clinical Laboratory**

For the treatment-emergent laboratory assessments, the observed values and change from baseline values of the continuous hematology, coagulation, and chemistry results will be summarized in SI units at each visit by treatment group.

The number and percentage of subjects meeting at least 1 threshold analysis criterion event during the TE Period for the Treatment Period will be summarized by treatment group. The threshold analysis criterion shift from baseline will also be summarized for select laboratory parameters. The threshold analysis criteria are provided in [Appendix](#) .

For select liver function laboratory tests (alanine transaminase [ALT], aspartate transaminase [AST], alkaline phosphatase [ALP], and total bilirubin), a scatterplot of the maximum TE value versus the baseline value corresponding to xULN (upper limit of normal) will be presented. Further, a scatterplot of the maximum TE value of ALT and AST, separately, versus the maximum TE value of total bilirubin corresponding to xULN will also be presented by treatment group. For ALT, AST, and total bilirubin, box-and-whisker plots will be used to display raw values at each visit by treatment group.

Results of positive serum/urine pregnancy tests will be listed in individual subject data listings only. For the positive serum pregnancy listing, subjects with serum HCG which are abnormally high will be selected.

In addition, listings containing individual subject hematology, chemistry, coagulation, and urinalysis values will be provided. The listings will include data from both scheduled and unscheduled visits. A listing of subjects who meet the criteria of [(ALT>3xULN or AST>3xULN) and TBILI>2xULN] at any visit will be provided. This listing will include data from all visits (including unscheduled visits) and present values for ALT, AST, ALP, and total bilirubin.

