#### **8.4.8 Supportive Safety Analysis**

##### **8.4.8.1 Adverse Events of Special Interest**

For this study, elevated transaminases, creatine kinase elevations, rash, cataracts, hypoglycemia, and neuropsychiatric events as determined by MedDRA PTs in [Appendix](#) are considered adverse events of special interest (AESI).

For AESI during the TE Period for the Treatment Period, the following categories will be summarized by treatment group:

- Subjects with events
- Subjects with events by maximum severity
- Subjects with events leading to treatment discontinuation
- Subjects with events leading to treatment interruption
- Subjects with related events
- Subjects with serious events
- Subjects with related serious events
- Subjects with events leading to death
- Duration of events
- Time-to-onset of first event

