## **11 LIST OF APPENDICES**

**Appendix A: Analysis Visit Windows for Safety and Efficacy Assessments**

**Table 11-1 Analysis Visit Windows for Safety and Efficacy Assessments**

Assessment	Visit 	Target Study Day	Analysis Visit Window  (in study days)
Safety Assessments			

 
• Pulse oximetry
 
• Serum chemistry
 
• Hematology (except HbA1c)
 
• Vital signs (excluding BMI, height, weight)
 
	Day 1 (Baseline)	1	≤1 Pre-dose
	Day 15	15	[1, 22]
	Week 4	29	(22, 43]
	Week 8	57	(43, 71]
	Week 12	85	(71, 99]
	Week 16	113	(99, 141]
	Week 24	169	(141, 211]
	Week 36	253	(211, 309]
	Week 52	365	(309, 379]
	Safety Follow-up	Not applicable	Use nominal visit
HbA1c (%)	Day 1 (Baseline)	1	≤1 Pre-dose
	Week 12	85	[1, 127]
	Week 24	169	(127, 267]
	Week 52	365	(267, 379]
Standard 12-lead ECG	Day 1 (Baseline)	1	≤1 Pre-dose
	Day 15	15	[1, 22]
	Week 4	29	(22, 43]
	Week 8	57	(43, 85]
	Week 16	113	(85, 141]
	Week 24	169	(141, 211]
	Week 36	253	(211, 309]
	Week 52	365	(309, 379]
		Safety Follow-up	Not applicable
Coagulation	Day 1 (Baseline)	1	≤1 Pre-dose
	Week 12	85	[1, 127]
	Week 24	169	(127, 211]
	Week 36	253	(211, 309]
	Week 52	365	(309, 379]
		Safety Follow-up	Not applicable
Efficacy Assessments			

 
• Spirometry (in-clinic)
 
• Height, weight, BMI, and z-scores
 
	Baseline	-	≤1 Pre-dose
	Day 15	15	[1, 22]
	Week 4	29	(22, 43]
	Week 8	57	(43, 85]
	Week 16	113	(85, 141]
	Week 24	169	(141, 211]
	Week 36	253	(211, 309]
	Week 52	365	(309, 379]
		Safety Follow-up	Not applicable

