**Table 11-6 Threshold Analysis Criteria for Laboratory Tests**

Parameter	Threshold Analysis	Comments
Clinical Chemistry (LFT)		
ALT or AST	>3xULN	For labeling purpose
	>5xULN	
	>8xULN	

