## Appendix G: Adverse Events of Special Interest

Table 11-7 MedDRA Preferred Terms for Event of Special Interest	
Adverse event of special interest	MedDRA preferred terms [1]
Transaminase Elevations	Alanine aminotransferase abnormal, Alanine aminotransferase increased, Aspartate aminotransferase abnormal, Aspartate aminotransferase increased, Transaminases abnormal, Transaminases increased, Liver function test abnormal, Liver function test increased, Hypertransaminasaemia, Hepatic enzyme abnormal, Hepatic enzyme increased
Rash	AGEP-DRESS overlap, Acute generalised exanthematous pustulosis, Anal rash, Cutaneous vasculitis, Dermatitis, Dermatitis allergic, Dermatitis atopic, Dermatitis bullous, Dermatitis exfoliative, Dermatitis exfoliative generalised, Drug eruption, Drug hypersensitivity, Drug reaction with eosinophilia and systemic symptoms, Epidermal necrosis, Epidermolysis, Erythema multiforme, Erythrodermic atopic dermatitis, Exfoliative rash, Fixed eruption, Generalised bullous fixed drug eruption, Immune-mediated dermatitis, Lichen planus pemphigoides, Mucocutaneous rash, Mucocutaneous toxicity, Nodular rash, Oculomucocutaneous syndrome, Penile dermatitis, Perioral dermatitis, Periorbital dermatitis, Rash, Rash erythematous, Rash follicular, Rash macular, Rash maculo-papular, Rash maculovesicular, Rash morbilliform, Rash papular, Rash papulosquamous, Rash pruritic, Rash pustular, Rash rubelliform, Rash scarlatiniform, Rash vesicular, SJS-TEN overlap, Scrotal dermatitis, Severe cutaneous adverse reaction, Skin exfoliation, Skin necrosis, Skin toxicity, Stevens-Johnson syndrome, Systemic contact dermatitis, Toxic epidermal necrolysis, Toxic skin eruption, Type IV hypersensitivity reaction, Urticaria, Urticaria papular, Urticaria vesiculosa, Urticarial dermatitis, Urticarial vasculitis, Vasculitic rash
Cataracts	Atopic cataract, Cataract, Cataract congenital, Cataract cortical, Cataract diabetic, Cataract nuclear, Cataract subcapsular, Lens discolouration, Lenticular opacities, MYH9-related disease, Radiation cataract, Toxic cataract
Hypoglycemia	Blood glucose decreased, Hypoglycaemia, Glycopenia, Hyperinsulinaemic hypoglycaemia, Hypoglycaemia unawareness, Hypoglycaemic coma, Hypoglycaemic encephalopathy, Hypoglycaemic seizure, Hypoglycaemic unconsciousness, Shock hypoglycaemic

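### Hypoglycaemia is an adverse event of special interest and glucose is measured throughout, but no by-arm table counts subjects with low glucose or shows a glucose shift

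*SAP*

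**What the plan says.** Protocol 12.3.4 names the AESIs: "LFT elevations, creatine kinase elevations, rash, cataracts, hypoglycemia, and neuropsychiatric events will be designated as AEs of special interest". SAP 8.4.8.1 repeats the list, with transaminases in place of LFTs, and says how events are found: "hypoglycemia, and neuropsychiatric events as determined by MedDRA PTs in" Appendix G. The hypoglycaemia terms there begin "Blood glucose decreased, Hypoglycaemia, Glycopenia".

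Glucose is in the serum chemistry panel of Protocol Table 11-2. Protocol Table 3-2 and the "Serum chemistry" windows of SAP Table 11-1 place that panel at Day 15 and Weeks 4, 8, 12, 16, 24, 36 and 52 after baseline.

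SAP 8.4.2 plans these outputs that could carry glucose:
- observed and change values for all continuous chemistry results, by visit and arm;
- a threshold table giving "The number and percentage of subjects meeting at least 1 threshold analysis criterion event during the TE Period for the Treatment Period", by arm;
- a shift in the threshold criterion for selected parameters;
- individual listings, including unscheduled visits.

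The limits for the second and third outputs are in SAP Appendix F. In Table 11-3, the block headed "Clinical Chemistry (NON-LFT" lists albumin, amylase, creatinine, lipase, total protein and creatine kinase. Table 11-6, annotated "For labeling purpose", covers ALT or AST only.

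**The concern.** Three AESIs have a direct serum chemistry measure: transaminase elevation, creatine kinase elevation and hypoglycaemia. For the first two, a reader of the study report will see reported events and, separately, how many subjects per arm crossed graded laboratory limits. For hypoglycaemia only the reported events are counted. Whether a low value becomes an event depends on the investigator's judgement of clinical significance, so the by-arm picture depends partly on reporting practice even though central-laboratory values are collected for all subjects on the same schedule. At stake is the completeness of the descriptive comparison for a safety event that the sponsor itself singled out.

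**Working it through.** The plan states no figure to reproduce. The check compares the panel with the threshold tables and then asks what each remaining output can show.

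**1. Coverage of the panel.** Protocol Table 11-2 lists 24 serum chemistry analytes, counting the three bilirubins separately. Thirteen have a criterion in SAP Table 11-3: ALT, AST, alkaline phosphatase, total, direct and indirect bilirubin, GGT, albumin, amylase, creatinine, lipase, total protein and creatine kinase. That leaves 24 - 13 = 11 without one: glucose, blood urea nitrogen, sodium, potassium, calcium, chloride, magnesium, bicarbonate, phosphate, cholesterol and lactate dehydrogenase. Glucose is the only one of the 11 that measures a designated AESI directly. Table 11-6 adds no analyte.

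**2. The three AESIs side by side.**

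| AESI | Preferred-term list (Appendix G) | Graded laboratory bands (Table 11-3) | By-arm count of subjects over or under a limit |
|---|---|---|---|
| Transaminases | Yes | Yes | Yes |
| Creatine kinase | Yes | Yes | Yes |
| Hypoglycaemia | Yes | No | No |

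A threshold shift needs a criterion, so without a glucose row there is no glucose shift either.

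**3. Amount of data.** 8 visits x 550 subjects = 4,400 scheduled post-baseline on-treatment values at most, or 8 x 275 = 2,200 per arm, before dropout and missed samples. This counts tests, not low values.

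**4. What the continuous summary can show.** SAP 8.1 defines it as n, mean, SD, median, minimum and maximum. The minimum is one subject's value per arm and visit, so it does not separate one low subject from twenty. The mean is insensitive to a small affected group. As an illustration only, assume that affected subjects' glucose falls by 2 mmol/L (not a figure from the documents). Then shift in arm mean = -2 x share affected:

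| Share of an arm of 275 | Subjects (rounded) | Shift in arm mean (mmol/L) |
|---|---|---|
| 2% | 6 | -0.04 |
| 5% | 14 | -0.10 |
| 10% | 28 | -0.20 |

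**5. Unscheduled values.** Under the notes to SAP Table 11-1, the value nearest the target day represents each window. A low unscheduled value further from that day is left out of the by-visit summary and remains only in the listings. SAP 8.1 does bring unscheduled values into treatment-emergent minima for safety analyses, but no glucose output in 8.4.2 is specified to use that minimum.

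**6. The adverse event route.** Protocol 11.6.2 requires abnormal, clinically significant laboratory results to be reported as adverse events. Protocol 13.1.1.2 ties significance to related signs or symptoms, further testing or intervention, or a change to study drug or discontinuation, and leaves the decision to the investigator. A low value meeting these conditions can reach the AESI table as Blood glucose decreased. An asymptomatic low value on which nobody acts need not.

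**The case against.** The strongest reply is that the plan does not neglect glucose. It is summarised by visit and arm, with the minimum and the largest fall from baseline shown. Every individual value is listed. Clinically significant low values become adverse events, and the AESI list includes a laboratory-type term to catch them. Reporting takes place under the blind. No section promises a laboratory threshold for each AESI, Table 11-3 is headed as a selected set, and safety analysis is descriptive only. Eight samples over 52 weeks, not timed to meals, are also a weak screen for an episodic event.

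Most of this stands, and it rules out several stronger readings that a reader might infer:
- That low glucose appears in no comparative table. It enters the by-visit, by-arm continuous summary.
- That individual low values cannot be seen. The visit minimum and the listings show them.
- That nobody checks the values against a low limit. The documents show only that no SAP threshold table does so; investigators must still assess laboratory results.
- That the plan contradicts itself, or that reporting differs by arm. Nothing in the documents supports either.

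The reply does not supply the missing count. A minimum, a mean and a listing do not say how many subjects in each arm had low glucose, and the adverse event route leaves out values judged not clinically significant.

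**Conclusion.** The point holds as a narrow gap in descriptive safety reporting. Followed as written, SAP 8.4.2 and Appendix F give no by-arm count of subjects with low glucose and no glucose shift, although the other two AESIs with a direct serum chemistry measure have graded bands. Low values judged not clinically significant are therefore not counted by arm.

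The size of the effect cannot be derived, because the documents give no expected number of low values; the 4,400 is only a ceiling on scheduled tests. The conclusion rests on reading Tables 11-3 and 11-6 as the full set of laboratory criteria, which is how SAP 8.4.2 uses Appendix F. The primary analysis, power and alpha are not affected. It is an optional, inexpensive improvement.

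**What to change.** Add a low-glucose row to SAP Table 11-3: below the lower limit of normal, plus graded bands from CTCAE, the system that the table already uses for many rows. The documents give no glucose cut-offs, so the sponsor should set them. Report:
- number and percentage of subjects in each category by arm during the TE Period for the Treatment Period, including unscheduled values;
- the shift from baseline;
- the number of subjects per arm with a low value but no hypoglycaemia AESI term.

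The cost is one row in an existing table, which already has lower-limit rows for albumin, hemoglobin and platelets, plus one cross-tabulation against the AESI flag. No new data are needed. The documents do not time chemistry samples to meals, so the table needs a footnote saying so. SAP section 3 allows amendment before database lock; after lock, the table could still be produced if labelled post hoc.

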**Table 11-3 Threshold Analysis Criteria for Laboratory Tests (as applicable)**

Parameter	Threshold Analysis	Comments
Coagulation		
Activated partial thromboplastin time (PTT)	>ULN - $\leq 1.5 \times \text{ULN}$ $>1.5 \times - \leq 2.5 \times \text{ULN}$ $>2.5 \times \text{ULN}$	CTCAE grade 1-3
Prothrombin time (PT) International Normalized Ratio (INR)	>ULN - $\leq 1.5 \times \text{ULN}$ $>1.5 \times - \leq 2.5 \times \text{ULN}$ $>2.5 \times \text{ULN}$	CTCAE grade 1-3

**Table 11-4 Threshold Analysis Criteria for ECGs**

Parameter	Threshold Analysis	Comments
HR	Bradycardia  $<50$ beats per minute (bpm) $<45$ bpm Decrease from baseline $\geq 10$ bpm Decrease from baseline $\geq 20$ bpm $<50$ bpm and decrease from baseline $\geq 10$ bpm $<50$ bpm and decrease from baseline $\geq 20$ bpm	Per HV grade 2, 3, plus shift change
	Tachycardia  $>100$ bpm $>115$ bpm $>130$ bpm Increase from baseline $\geq 10$ bpm Increase from baseline $\geq 20$ bpm $>100$ bpm and increase from baseline $\geq 10$ bpm $>100$ bpm and increase from baseline $\geq 20$ bpm	Per HV grade 1, 2, 3, plus shift change
PR	$\geq 240$ msec $\geq 300$ msec $\geq 200$ msec and increase from baseline $\geq 40$ msec $\geq 200$ msec and increase from baseline $\geq 100$ msec	
	QRS  $>110$ msec $>160$ msec Increase from baseline $\geq 20$ msec Increase from baseline $\geq 40$ msec	
QTc	$>450$ msec and $<500$ msec (Male); $>470$ msec and $<500$ msec (Female) $\geq 500$ msec	To be applied to any kind of QT correction formula.
	Increase from baseline $>10$ msec Increase from baseline $>20$ msec Increase from baseline $>40$ msec Increase from baseline $>60$ msec	

**Table 11-4 Threshold Analysis Criteria for ECGs**

Parameter	Threshold Analysis	Comments
-----------	--------------------	----------

Note: Based on CPMP 1997 guideline.

**Table 11-5 Threshold Analysis Criteria for Vital Signs**

Parameter	Threshold Analysis	Comments
-----------	--------------------	----------

Pulse Rate	Same as above in ECG category	
SBP increased	>140 mmHg >160 mmHg >10 mmHg increase from baseline >20 mmHg increase from baseline  >140 mmHg & >10 mmHg increase from baseline >140 mmHg & >20 mmHg increase from baseline >160 mmHg & >10 mmHg increase from baseline >160 mmHg & >20 mmHg increase from baseline	809/770 analyses
SBP decreased	<90 mmHg <80 mmHg >10 mmHg decrease from baseline >20 mmHg decrease from baseline  <90 mmHg and >10 mmHg decrease from baseline <90 mmHg and >20 mmHg decrease from baseline <80 mmHg and >10 mmHg decrease from baseline <80 mmHg and >20 mmHg decrease from baseline	Per HV grade 1, 3, plus shift change
DBP increased	>90 mmHg >100 mmHg >5 mmHg increase from baseline >10 mmHg increase from baseline  >90 mmHg and >5 mmHg increase from baseline >90 mmHg and >10 mmHg increase from baseline >100 mmHg and >5 mmHg increase from baseline >100 mmHg and >10 mmHg increase from baseline	
DBP decreased	<60 mmHg <45 mmHg >5 mmHg decrease from baseline >10 mmHg decrease from baseline  <60 mmHg and >5 mmHg decrease from baseline <60 mmHg and >10 mmHg decrease from baseline <45 mmHg and >5 mmHg decrease from baseline <45 mmHg and >10 mmHg decrease from baseline	

**Table 11-5 Threshold Analysis Criteria for Vital Signs**

Parameter	Threshold Analysis	Comments
Weight	Weight gain	CTCAE grade 1-3
	≥5% increase from baseline	
	≥10% increase from baseline	
	≥20% increase from baseline	CTCAE grade 1-3
	Weight loss	
	≥5% decrease from baseline	
≥10% decrease from baseline		
	≥20% decrease from baseline	

**Table 11-6 Threshold Analysis Criteria for Laboratory Tests**

Parameter	Threshold Analysis	Comments
Clinical Chemistry (LFT)		
ALT or AST	>3xULN	For labeling purpose
	>5xULN	
	>8xULN	

## Appendix G: Adverse Events of Special Interest

Table 11-7 MedDRA Preferred Terms for Event of Special Interest	
Adverse event of special interest	MedDRA preferred terms [1]
Transaminase Elevations	Alanine aminotransferase abnormal, Alanine aminotransferase increased, Aspartate aminotransferase abnormal, Aspartate aminotransferase increased, Transaminases abnormal, Transaminases increased, Liver function test abnormal, Liver function test increased, Hypertransaminasaemia, Hepatic enzyme abnormal, Hepatic enzyme increased
Rash	AGEP-DRESS overlap, Acute generalised exanthematous pustulosis, Anal rash, Cutaneous vasculitis, Dermatitis, Dermatitis allergic, Dermatitis atopic, Dermatitis bullous, Dermatitis exfoliative, Dermatitis exfoliative generalised, Drug eruption, Drug hypersensitivity, Drug reaction with eosinophilia and systemic symptoms, Epidermal necrosis, Epidermolysis, Erythema multiforme, Erythrodermic atopic dermatitis, Exfoliative rash, Fixed eruption, Generalised bullous fixed drug eruption, Immune-mediated dermatitis, Lichen planus pemphigoides, Mucocutaneous rash, Mucocutaneous toxicity, Nodular rash, Oculomucocutaneous syndrome, Penile dermatitis, Perioral dermatitis, Periorbital dermatitis, Rash, Rash erythematous, Rash follicular, Rash macular, Rash maculo-papular, Rash maculovesicular, Rash morbilliform, Rash papular, Rash papulosquamous, Rash pruritic, Rash pustular, Rash rubelliform, Rash scarlatiniform, Rash vesicular, SJS-TEN overlap, Scrotal dermatitis, Severe cutaneous adverse reaction, Skin exfoliation, Skin necrosis, Skin toxicity, Stevens-Johnson syndrome, Systemic contact dermatitis, Toxic epidermal necrolysis, Toxic skin eruption, Type IV hypersensitivity reaction, Urticaria, Urticaria papular, Urticaria vesiculosa, Urticarial dermatitis, Urticarial vasculitis, Vasculitic rash
Cataracts	Atopic cataract, Cataract, Cataract congenital, Cataract cortical, Cataract diabetic, Cataract nuclear, Cataract subcapsular, Lens discolouration, Lenticular opacities, MYH9-related disease, Radiation cataract, Toxic cataract
Hypoglycemia	Blood glucose decreased, Hypoglycaemia, Glycopenia, Hyperinsulinaemic hypoglycaemia, Hypoglycaemia unawareness, Hypoglycaemic coma, Hypoglycaemic encephalopathy, Hypoglycaemic seizure, Hypoglycaemic unconsciousness, Shock hypoglycaemic
Creatine Kinase Elevations	Blood creatine phosphokinase increased, Blood creatine phosphokinase MM increased, Blood creatine phosphokinase MB increased, Blood creatine phosphokinase BB increased, Muscle enzyme increased, Rhabdomyolysis, Myoglobinuria, Myoglobin urine present
Neuropsychiatric Events	Abnormal behaviour, Adjustment disorder with anxiety, Adjustment disorder with depressed mood, Adjustment disorder with mixed anxiety and depressed mood, Aggression, Agitated depression, Anger, Anhedonia, Anticipatory anxiety, Antisocial behaviour, Anxiety, Anxiety disorder, Assisted suicide, Attention deficit hyperactivity

	disorder, Behaviour disorder, Behavioural insomnia of childhood, Belligerence, Brain fog, Childhood depression, Completed suicide, Decreased interest, Depressed mood, Depression, Depression suicidal, Depressive symptom, Discouragement, Disturbance in attention, Dysania, Dysphoria, Feeling abnormal, Feeling guilty, Feeling of despair, Feelings of worthlessness, Generalised anxiety disorder, Helplessness, Hostility, Illness anxiety disorder, Initial insomnia, Insomnia, Intentional overdose, Intentional self-injury, Irritability, Major depression, Memory impairment, Mental disorder, Mental fatigue, Middle insomnia, Mixed anxiety and depressive disorder, Paradoxical insomnia, Persistent depressive disorder, Physical abuse, Physical assault, Poisoning deliberate, Psychophysiologic insomnia, Self-injurious ideation, Suicidal behaviour, Suicidal ideation, Suicide attempt, Suicide threat, Suspected suicide, Suspected suicide attempt, Terminal insomnia
[1] The preferred terms (PTs) listed in the table are based on the MedDRA version applicable at the time of finalization of the SAP. If the MedDRA version is upgraded at the time of the analysis, the corresponding PTs based on the upgraded version will be used in the analysis of adverse events of special interest.
